**Treatment schedules:**

**INO dosage**

- In **term babies**, gestational age equal to or greater than 34 weeks, the trial starting (and maximal) dosage of INO is 20 ppm, which would then be weaned down, after a 1 hour stabilisation period, to the minimum necessary dosage to sustain a clinically significant response. A response is defined as an increase in post ductal PaO2 of more than 3 kPa (22.5 mmHg) in the initial 15 minutes of giving INO. The ventilation should remain constant during this initial 15 minutes to prevent outside factors influencing the response.
- In **preterm babies**, gestational age less than 34 weeks, a dose response study is being undertaken to determine the most effective dose. The study will include doses from 5 to 40 ppm. Doses above 40 ppm will not be used.
- For centres not in the dose response study, until the results of the dose response study are available, a dose level starting at 5 ppm will be used. If no satisfactory response is achieved, the dose will be doubled to 10 ppm, then if necessary doubled again to 20 ppm, then again if required to 40 ppm. If at any point, after having achieved a response (an increase in post ductal PaO2 of more than 3 kPa (22.5 mmHg)), an increase in dose does not produce a further

significant increase in the response, then the dose should be dropped down to the previous level and maintained at that level.

- In **all babies** it is essential that after a period of stabilisation, for the INO dose to be maintained at the lowest possible effective level. Failure to ensure the lowest possible INO dose will result in increased INO and ventilator dependence. It is suggested that reverse dose response weaning is undertaken. This means that the INO dose is repeatedly reduced by approximately 10% every 2-3 minutes until a decrease (2-3 %) in oxygen saturations is noted. The INO should then be increased to the level it was at prior to the decrease in oxygenation. This should be re-evaluated every 12 hours.
- **Non responder** are those babies not showing an increase in post ductal PaO2 of more than 3 kPa (22.5 mmHg) in the initial 15 minutes of giving INO. Continue on INO, at 5 ppm, for 12 hours and then if there is still no response they should be weaned off INO. Weaning should be carried out in a reverse dose response fashion.
- Some babies, even some of those who appear not to have responded to INO, remain dependant on the INO, so that doses as low as 0.3 ppm may be required for a few days during the final weaning process.
- When **weaning** INO is withdrawn completely it may help to temporarily increase the FiO2 by up to 40% to finally wean the INO, especially in difficult cases.
- The INO administration circuit should remain attached to the ventilator for a further 24 hours to ensure stability after successful weaning from INO.

N.B. If a baby is randomized to 'the ventilatory support without INO' group, he or she should not receive INO at a later stage i.e. there should be no 'cross-over'.

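### For preterm babies outside the dose response study, two dosing rules give opposite instructions when there is no response to INO in the first 15 minutes

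*Protocol*

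**What the plan says.** All the relevant text is in the Protocol, Methods, Treatment schedules, under INO dosage.

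- **Babies of 34 weeks or more.** "the trial starting (and maximal) dosage of INO is 20 ppm". After an hour of stabilisation the dose is weaned to the least that sustains a clinically significant response. A response is a rise in post-ductal PaO2 of more than 3 kPa within the first 15 minutes.
- **Preterm babies in the dose response study.** "The study will include doses from 5 to 40 ppm. Doses above 40 ppm will not be used".
- **Preterm babies elsewhere (escalation rule).** "For centres not in the dose response study, until the results of the dose response study are available, a dose level starting at 5 ppm" applies. Then: "If no satisfactory response is achieved, the dose will be doubled to 10 ppm", and "then if necessary doubled again to 20 ppm, then again if required to 40 ppm". The rule follows directly on the preterm item, and its 40 ppm ceiling is the preterm ceiling. It repeats the 3 kPa threshold for a response but attaches no time limit to it.
- **Non-responders.** This rule names no gestational stratum and no type of centre. It covers babies without a rise of more than 3 kPa "in the initial 15 minutes of giving INO. Continue on INO, at 5 ppm, for 12 hours", with weaning to follow if there is still no response.

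**The concern.** A clinician at a centre outside the dose response study, with a preterm baby who has not responded to 5 ppm after 15 minutes, finds two instructions. One is to double the dose. The other is to stay at 5 ppm for 12 hours. Both cannot be followed.

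The protocol itself treats exposure as consequential. The Background section raises toxicity, including harm to lung tissue and a bleeding risk. The dosing section warns that failing to keep the dose as low as possible increases dependence on INO and on the ventilator. Time on ventilatory support and time on supplemental oxygen are secondary outcomes. Exposure among non-responders should therefore not depend on which item of the dosing section a centre happens to apply.

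**Working it through.** This is a comparison of stated rules, with a little arithmetic for size.

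**1. The stated figures are internally sound.** 3 kPa × 7.5 mmHg per kPa = 22.5 mmHg, as printed. The doubling series is 5 × 2 = 10, 10 × 2 = 20, 20 × 2 = 40 ppm, which stops at the preterm ceiling. The problem is not a numerical slip.

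**2. One preterm baby under both rules.** Take a baby of less than 34 weeks, at a centre outside the dose response study, before that study has reported, on 5 ppm, with a PaO2 rise of 3 kPa or less at 15 minutes.

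| | Escalation rule | Non-responder rule |
|---|---|---|
| Does the baby qualify? | Yes: no satisfactory response at 5 ppm | Yes: no qualifying rise in the first 15 minutes |
| Next dose | 10 ppm | 5 ppm |
| Highest dose reachable | 40 ppm | 5 ppm |
| Time per step | Not stated | 12 hours at 5 ppm, then wean if still no response |
| Precedence over the other rule | Not stated | Not stated |

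The ratio of the highest doses is 40 / 5 = 8.

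**3. A late responder.** Suppose the first rise above 3 kPa comes after a doubling, once the first 15 minutes have passed. Under the escalation rule, which sets no time limit, this baby has responded. Under the non-responder definition, which is tied to the start of INO, the same baby is a non-responder.

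**4. Babies of 34 weeks or more.** Escalation does not apply to them, because 20 ppm is both their start and their maximum. A baby in this stratum with no response at 15 minutes is on 20 ppm, yet the non-responder rule speaks of continuing at 5 ppm, a quarter of that dose (5 / 20 = 0.25). No step from 20 to 5 ppm is described.

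**5. How many babies.** The planned preterm total is about 200. Assuming equal allocation, the INO arm has 200 / 2 = 100. The babies under both rules are those 100, less the babies at dose response centres, less those treated after that study reports, less those who respond within 15 minutes. The protocol gives none of these shares, so 100 is a ceiling and no estimate is possible. For the same reason no effect on power can be calculated.

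**The case against.** The best defence is that the rules are sequential: titrate upwards and, if nothing works, return to 5 ppm, hold for 12 hours and wean. The order of the items fits this. The escalation rule does not say what to do with a baby who never responds, and the non-responder rule would fill that gap. For mature babies, who start at 20 ppm, the 5 ppm instruction can only mean stepping down after a failed starting dose, and one could read it the same way for preterm babies.

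This reading is possible but is not stated, and the wording sits badly with it. Non-response is fixed by the first 15 minutes of INO, not by failure at the top step, and a baby who has been taken to 40 ppm cannot continue at 5 ppm. The Trial Folder, through which centres are taken before they recruit, may settle the order. It is not shown, and the protocol would still contradict itself.

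A reader might infer more than this, and on four points the documents do not support it:

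- *Escalation to 40 ppm concerns every non-responder.* It is confined to preterm babies at centres outside the dose response study, until that study reports.
- *The hour at the starting dose ("which would then be weaned down, after a 1 hour stabilisation period") also conflicts with the 15-minute rule in mature babies.* That weaning aims at the least dose that sustains a response, so it presupposes one. The mismatch in this stratum is only the one between 20 and 5 ppm.
- *The two rules disagree on withdrawal at 12 hours.* The escalation rule is silent on withdrawal after failure at the top dose, so it sets no opposing rule. Twelve hours is when weaning starts, and the protocol expects some apparent non-responders to need very low doses for a few days.
- *The trial therefore tests no defined policy, and a null result could not be read.* The aim is to compare adding with not adding INO, dose varies by design, and analysis is by allocated group.

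**Conclusion.** The point holds in a limited form. For preterm babies at centres outside the dose response study, until its results are available, the protocol gives two incompatible instructions for no response to 5 ppm in the first 15 minutes. It sets no order between them and no step duration, and it classifies late responders in two ways. For babies of 34 weeks or more, there is a separate mismatch between the 20 ppm start and the 5 ppm wording.

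The consequence is that exposure of INO-arm non-responders can differ between centres that all comply, with a highest dose of 5 or 40 ppm. This bears on safety and on how the regimen is described, reproduced and interpreted. It does not undermine the randomised comparison.

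The conclusion on the conflict rests on the wording alone. The ceiling of about 100 preterm babies rests on equal allocation, and the true number is smaller and unknown. The contradiction is worth correcting because it concerns exposure and is easily resolved, but it is not a flaw in the design of the comparison.

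**What to change.** The clinical leads should reconcile these passages and state:

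1. for each gestational stratum, which rule governs a baby with no response in the first 15 minutes;
2. whether the 15-minute window restarts at each dose step, which also settles how a late responder is classed;
3. for babies of 34 weeks or more, how the non-responder wording relates to the starting dose.

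The clarified wording should then go to all centres. No view is taken here on which dose or rule is right.

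The cost is a wording change and a notice to centres. Sample size, randomisation and analysis are unaffected. It would help to confirm that part C of the datasheet, completed for all babies, shows which path was followed. Its fields are not shown, so whether anything needs adding cannot be judged from the protocol.

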### **Data collection:**

Data will be collected at five points in time.

#### 1. At trial entry

Complete part A of the datasheet before telephoning the randomization service and then complete part B of the datasheet as soon as possible after trial entry. Make 2 photocopies of both part A and part B. Pass one of the copies to the local trial neonatal co-ordinator and send the other copy to The INNOVO Trial Data Co-ordinating Centre in the FREEPOST envelope provided in the trial folder. Attach an INNOVO Trial sticker to the baby's notes and place the original datasheet into the baby's notes.

#### 2. At administration of nitric oxide, if relevant. (this part to be completed for all babies whether or not nitric oxide is administered).

Complete part C of the trial datasheet, make 2 photocopies. Pass one of the copies to the local trial neonatal co-ordinator and send the other copy to The INNOVO Trial Data Co-ordinating Centre in the FREEPOST envelope provided. If the baby is also enrolled in the dose response study, take the next one from the box of sequentially arranged envelopes.

#### 3. At 7 days after trial entry

A cerebral ultrasound scan should be performed 7 days after trial entry. Complete part D of the datasheet, make 2 photocopies. Pass one of the copies to the local trial neonatal co-ordinator and send the other copy to The INNOVO Trial Data Co-ordinating Centre in the FREEPOST envelope provided.

4. At discharge home, transfer to another hospital, death or 3 months of age, whichever is soonest

Ensure a cerebral ultrasound is carried out at 36 weeks gestational age (for babies <34 completed weeks gestation at birth) or discharge from hospital (for babies =34 completed weeks gestation at birth) and complete part E of the datasheet.

Complete parts F and G of the datasheet. Make a photocopy of parts E, F and G. Pass the photocopy to the local trial neonatal co-ordinator and send the complete original datasheet to The INNOVO Trial Data Co-ordinating Centre in the FREEPOST envelope provided.

While the baby is in hospital, the local neonatal co-ordinator or named nurse will be contacted regularly by the Data Co-ordinating Centre for brief details about the progress of the baby.

If the baby is transferred to another hospital, please let the staff at the transfer hospital know that the baby is in The INNOVO Trial and that they will be contacted by the Data Co-ordinating Centre.

If the baby dies, follow your usual procedures. If possible, seek consent from the parents for a post-mortem examination, ideally by a paediatric pathologist following Confidential Enquiry into Stillbirths and Deaths in Infancy (CESDI) guidelines and inform the pathologist that the baby is in The INNOVO Trial. The name of your local pathologist is found on the inside back cover of the trial folder, and full details of the pathology study are given in the Trial Folder. A copy of the Stillbirth and Neonatal Death Society (SANDS) *Guidelines for Professionals* is found in the Trial Folder along with copies of the following leaflets: *Support for you when your baby dies* (the SANDS introductory leaflet), *Mainly for fathers* and a copy of *Saying Goodbye to your baby*.

For centres taking part in the toxicology study, broncho-alveolar lavage fluid from babies randomized in both arms of the trial will be collected.

5. At one year of age (corrected)

Surviving children will be seen by their local paediatricians who will be asked to complete a trial follow-up datasheet.

Eligible babies will be invited to participate in respiratory function tests. These tests will take place at one of two centres (Hospital for Sick Children at Great Ormond Street, or Leicester Royal Infirmary). Arrangements will be made to pay parents' travel expenses.

Further follow-up is the subject of a separate protocol.

### **Sample size:**

The size of the trial is calculated separately for babies born preterm, and 'mature' babies based on data from the pilot trial.

- a) Preterm babies: To detect whether INO reduces the primary outcome of death or severe disability at one year (corrected) from 60% to 40% (i.e. RR of 0.67) with  $\alpha$  of 0.05 (2-sided) and 80% power would require a total sample size of approximately 200 babies, which would also allow us to detect a reduction in the short term outcome from 75% to 55%.
- b) 'Mature' babies: Assuming recruitment of 'mature' babies ceases at the same time as for preterm babies, a further 86 'mature' babies are likely to have been recruited. The total sample size of 110 (including the 24 recruited in 1997/8) could detect whether INO could reduce the primary outcome of death or severe disability at one year (corrected) from 31.5% to 8.5% (i.e. RR of 0.27) with  $\alpha$  of 0.05 (2-sided) and 80% power, although recruitment of 110 'mature' babies would be sufficient to detect a reduction in the short term outcome from 70% to 40%.

### **Interim analysis:**

An independent Data Monitoring Committee (DMC) has already reviewed, in strict confidence, the results of the pilot trial. In the main trial, the DMC will consider at least one further interim analysis of the main trial. In the light of these data, and other evidence from relevant studies, the DMC will inform the Steering Committee, if in their view i) there is proof beyond reasonable doubt that the data indicate that any part of the protocol under investigation is either clearly indicated or contra-indicated, either for all babies or for a particular subgroup, or ii) it is evident that no clear outcome will be obtained with the current trial design. Unless modification or cessation of the protocol is recommended by the DMC, the Steering Committee, collaborators and administrative staff (except those who supply the confidential information) will remain ignorant of the results of the interim analysis.

---

